11.3 Toxicity Monitoring

Telotristat is an FDA approved drug for management of diarrhea in patients with carcinoid syndrome in patients who are on SSAs. The FDA approved dose is 250 mg to be taken by mouth with meals three times daily. In this study we will also be using telotristat in patients with carcinoid syndrome but with a dose of 500mg three times daily. Both dosing regimens (250mg TID and 500 mg TID) were used in the phase 3 TELESTAR trial along with a companion phase 3 trial, TELECAST, which assessed the safety and efficacy of telotristat ethyl in patients with carcinoid syndrome during a 12-week double-blind treatment period followed by a 36-week open-label extension (OLE). The overall incidence of treatment related adverse events was similar among all groups. During a 12 week period, 5 patients (19.2%) in the placebo group experienced a serious adverse event (SAE), whereas only 1 patient (4.0%) and 3 patients (12.0%) experienced a SAE in the telotristat ethyl 250 mg and telotristat ethyl 500 mg groups.

Given the safety and efficacy of this FDA approved drug has been established we will not be conducting toxicity monitoring (Pavel et al. doi: 10.1530/ERC-17-0455).

12.0 Reporting Requirements

Data and safety monitoring will be conducted by MD Anderson Cancer Center DSMB.

12.1 Adverse Event Reporting

These guidelines serve to bring the Department of Cardiology in compliance with the institutional policy on Reporting of Serious Adverse Events-definition of expected AE-“All clinical protocols should include a list of the expected and anticipated events or hospitalizations relating to the study treatment” and Guideline for Good Clinical Practice 4.11.1

An adverse event is the appearance or worsening of any undesirable sign, symptom, or medical condition occurring after the first protocol intervention, even if the event is not considered to be related to study treatment. Medical conditions/diseases present before starting study therapy are only considered adverse events if they worsen after starting study treatment. Abnormal laboratory values or test results constitute adverse events only if they induce clinical signs or symptoms, are considered clinically significant, or require therapy.

Adverse event is any untoward medical occurrence that may present during treatment with a pharmaceutical product but which does not necessarily have a causal relationship with this treatment.

Adverse drug reaction is a response to a drug which is noxious and unintended and which occurs at doses normally used in man for prophylaxis, diagnosis, or therapy of disease or for the modification of physiologic function.

Assessing causal connections between agents and disease is fundamental to the understanding of adverse drug reactions. In general, a drug may be considered a contributory cause of an adverse event if, had the drug not been administered, 1) the event would not have happened at all, 2) the event would have occurred later than it actually did, or 3) the event would have been less severe.

For each AE, the Investigator will assess the causal relationship between each of the study drugs and the AE using their clinical expertise and judgment according to the most appropriate description as follows:

- **Not related:** The AE does not follow a reasonable temporal relationship to administration of the study drug, or an alternative etiology (eg, underlying disease, complications, concomitant drugs, or concurrent treatment) is more likely
- **Unlikely related:** The AE has an improbable temporal relationship to administration of the study drug, or an alternative etiology (eg, underlying disease, complications, concomitant drugs, or concurrent treatment) is more likely
- **Possibly related:** The AE follows a reasonable temporal relationship to administration of the study drug (including the course after withdrawal of the drug), and an alternative etiology (eg, underlying disease, complications, concomitant drugs, or concurrent treatment) is equally or less likely
- **Probably related:** The AE follows a reasonable temporal relationship to administration of the study drug (including the course after withdrawal of the drug), and an alternative etiology (eg, underlying disease, complications, concomitant drugs, or concurrent treatment) is unlikely
- **Definitely related:** The AE follows a plausible temporal relationship to administration of the study drug (including the course after withdrawal of the drug) and alternative etiology (eg, underlying disease, complications, concomitant drugs, or concurrent treatment) can be ruled out. Positive rechallenge (ie, reappearance or worsening of the AE after study drug is reintroduced) or a response pattern known to be associated with administration of the study drug provides further evidence of a definitive causality assessment.

Adverse Events (AEs) will be evaluated according to CTC version 5 in each protocol. AEs will be documented in an AE log. Prometheus will be used to enter data for this protocol. The Investigator or physician designee is responsible for verifying and providing source documentation for all adverse events and assigning the attribution for each event for all subjects enrolled on the trial.

Severity of the adverse events (AEs) -The severity of the adverse events (AEs) will be graded according to the National Cancer Institute Common Terminology Criteria for Adverse Events (NCI CTCAE) V.05. Events not included in the NCI CTCAE will be scored as follows:

General grading:

- Grade 1: Mild: discomfort present with no disruption of daily activity, no treatment required beyond prophylaxis.

- Grade 2: Moderate: discomfort present with some disruption of daily activity, require treatment.
- Grade 3: Severe: discomfort that interrupts normal daily activity, not responding to first line treatment.
- Grade 4: Life Threatening: discomfort that represents immediate risk of death

Recommended Adverse Event Recording Guidelines

Attribution	Grade 1	Grade 2	Grade 3	Grade 4	Grade 5
Unrelated	Phase I	Phase I	Phase I	Phase I	Phase I
			Phase II	Phase II	Phase II
				Phase III	Phase III
Unlikely	Phase I	Phase I	Phase I	Phase I	Phase I
			Phase II	Phase II	Phase II
				Phase III	Phase III
Possible	Phase I	Phase I	Phase I	Phase I	Phase I
	Phase II	Phase II	Phase II	Phase II	Phase II
		Phase III	Phase III	Phase III	Phase III
Probable	Phase I	Phase I	Phase I	Phase I	Phase I
	Phase II	Phase II	Phase II	Phase II	Phase II
		Phase III	Phase III	Phase III	Phase III
Definitive	Phase I	Phase I	Phase I	Phase I	Phase I
	Phase II	Phase II	Phase II	Phase II	Phase II
		Phase III	Phase III	Phase III	Phase III

Expected events during carcinoid syndrome and carcinoid heart disease therapy are:

- Nausea
- Headache
- Edema
- Flatulence
- Pyrexia
- Decreased appetite
- Fatigue
- Flushing
- Diarrhea
- Constipation
- Abdominal pain
- electrolyte abnormalities (sodium, potassium, CO₂, magnesium)

- m. chemistry abnormalities (LDH, phosphorus, calcium, BUN, protein, albumin, uric acid, alkaline phosphatase, glucose)
- n. coagulation abnormalities
- o. bone, joint, or muscle pain
- p. liver function test abnormalities associated with infection or disease progression
- q. disease progression
- r. volume overload
- s. signs and symptoms of heart failure
- t. arrhythmias such as atrial fibrillation, atrial flutter, and supraventricular tachycardia
- u. development of depression - **patients with depression and suicidal ideation will be referred immediately to psychiatry services as per institutional guidelines **

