6.2.2 Study Overview

Study Type: Prospective Clinical Trial

Enrollment: 79 participants

Allocation: Randomized 1: 1

Intervention Model Description: Participants were randomized to one of two treatment arms by stratified randomization method. Those who were randomized to treatment arm would

receive telotristat ethyl 500 mg po TID + SSA and those who were randomized to placebo arm would receive placebo + SSA

Blinding: Double (Participant and Investigators)

Primary Purpose: Treatment and disease progression

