6.3.2 Dose Adjustments for adverse events related to the study drug

Adverse Events will be graded as follows (NCI CTCAE version 5.0)

Grade 1 No change in dose
Grade 2 Hold until ≤Grade 1. Resume at same dose level.
Grade 3 Hold until ≤Grade 1. Resume at 1 dose level lower (250 mg tid).
Grade 4 Hold and contact the Primary Investigator

Dose can also be adjusted or discontinued per PI's discretion for patients' safety.

*Patients unable to tolerate 250 mg tid should be discontinued from telotristat ethyl. **Constipation and abdominal pain dose adjustment is different (see below)

6.3.3 Recommended management for the following AEs:**6.3.3.1** Nausea and/or vomiting: treatment with antiemetics**6.3.3.2** Diarrhea: treat underlying cause and/or with antidiarrheal**6.3.3.3** Gastrointestinal toxicity**6.3.3.3.1** Monitor concomitant medication usage**6.3.3.3.2** Constipation (Grade 1 and above): initiate treatment as clinically indicated; examples of therapies include: laxatives, enemas, suppositories, psyllium hydration, over-the-counter (OTC) agents**6.3.3.3.3** Abdominal pain (Grade 1 and above): initiate treatment as clinically indicated; examples of therapies) include: analgesics, anti-gas/bloating agents**6.3.3.3.4** Hold telotristat ethyl for Grade 2 constipation or abdominal pain until \leq Grade 1.**6.3.3.3.5** Discontinue telotristat ethyl for Grade 3 constipation or abdominal pain*(please note this is different than above table)**6.3.3.4** Suicidal ideation: discontinue telotristat ethyl**6.4 Treatment Compliance**

Patients will be asked to bring their unused or unopened bottles of telotristat ethyl to each visit. Patients will be allowed to ship their unused and/or unopened bottles of telotristat ethyl back to PI at MDAnderson if traveling is impossible/restricted. At each visit study site personnel will count returned tablets and reconcile the counts against planned number of doses for that interval. All dosages prescribed and dispensed to the patient, dose modification(s), and missed dose(s), including planned dose interruptions during the study must be recorded. Site personnel are to clarify any discrepancy and record this information.

Patients must maintain at least 70% compliance at clinical visits (3 month interval including allowed window; see section 8 for details) in dosing to be deemed as compliant.

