11.2 Statistical Analysis Plan

We will analyze two analysis sets, including modified intention-to-treat and per protocol analysis sets. Modified intention-to-treat analysis set will include all patients who were randomized and started a study treatment, regardless of whether they received treatment as planned. Per protocol analysis set will include all patients who received treatment as planned.

Patient baseline characteristics and outcome variables (primary endpoint and secondary endpoints (absolute changes and percent changes for continuous endpoints)) will be summarized by study arm, using mean (standard deviation (SD)) or median (inter quartile range (IQR)) for continuous variables and frequency (%) for categorical variables. Repeatedly measured variables will be summarized using descriptive statistics by study arm and by time point (baseline, 3 months, and 6 months). The mean percent

change in NT-proBNP at 6 months from baseline will be estimated in each arm along with the standard deviation. The mean percent change in NT-proBNP will be compared between 2 arms by two-sample t-test. Linear regression model will be used to compare the 2 arms in the mean percent change, adjusting for stratification factors. Those without 3-months or 6-months NT-proBNP may be imputed, using last observation carried forward method or other methods.

Compliance is defined as the total number of medications taken divided by the total number of medications provided during 6 month treatment period. The proportion of patients maintaining at least 70% compliance will be estimated in each arm. Proportion of patients experiencing each type of side effects will be estimated in each arm along with 95% confidence interval (CI). The change from baseline to 3 months and the change from baseline to 6 months in variables described in secondary objectives will be compared within each arm by paired t-test or Wilcoxon signed-rank test for continuous variables and Mantel-Haenszel test for categorical variables. Generalized linear mixed effects models will be used to compare two arms in repeatedly measured outcomes over time. P-values less than 0.05 will indicate statistical significances. SAS 9.4 (Cary, NC) and other relevant software will be used for statistical analysis.

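### The recommended adverse-event recording table conflicts with the protocol's all-event definition, log and follow-up rules, so low-grade events may go unrecorded and the per-arm side-effect proportions may depend on attribution

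*Combined protocol and SAP*

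**What the plan says.** Section 12.1 defines an adverse event to include any new or worsening sign, symptom or condition, "even if the event is not considered to be related to study treatment". It then states that "AEs will be documented in an AE log" and makes the investigator or physician designee responsible for "providing source documentation for all adverse events and assigning the attribution for each event for all subjects enrolled on the trial". Section 12.5 asks for follow-up of all AEs. None of these sentences excludes an event by grade or attribution.

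The same section then gives a table headed "Recommended Adverse Event Recording Guidelines". Its rows are attribution categories, its columns are Grades 1 to 5, and each cell lists the trial phases for which such an event is recorded. Low-grade cells leave out Phase II, Phase III or both.

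Two other places rely on what is recorded:

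- Section 6.3.3.3.4 reads "Hold telotristat ethyl for Grade 2 constipation or abdominal pain until" Grade 1 or lower. The next item discontinues the drug for Grade 3 constipation or abdominal pain. Neither sentence mentions attribution.
- Section 11.2 gives the planned safety summary: "Proportion of patients experiencing each type of side effects will be estimated in each arm along with 95% confidence interval (CI"). It does not say whether side effects means all AEs or only those judged related.

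**The concern.** Two staff members could both follow Section 12.1 and record different events. One enters every AE in the log. The other applies the table and omits low-grade events judged not to be due to the study drug.

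The filter falls where attribution is hardest. Every patient has a history of carcinoid syndrome and is on a somatostatin analog (5.1.3, 5.1.4). Under 12.1, an event is Not related or Unlikely when another cause, such as underlying disease or concomitant drugs, is more likely. Constipation, abdominal pain, diarrhea, flushing and depression all appear in the protocol's list of events expected during therapy for this disease.

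In a randomised, double-blind, placebo-controlled trial, comparing all events by arm addresses causality without relying on case-by-case judgement. Filtering on that judgement first gives up this advantage. The 11.2 proportions are the only planned per-arm safety summary. Section 11.3 plans no toxicity monitoring, and the study dose is 500 mg three times daily against an approved 250 mg. The DSMB named in 12.0 can review only what has been recorded.

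**Working it through.** The plan states no AE rate or safety-precision figure, so there is none to reproduce. The check is a count of table cells, followed by a trace of what each reading does to an event.

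**Inputs.** Five attributions by five grades give 25 cells (table in 12.1). The lowest grade recorded is:

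| Attribution | Phase I | Phase II | Phase III |
|---|---|---|---|
| Unrelated, Unlikely | 1 | 3 | 4 |
| Possible, Probable, Definitive | 1 | 1 | 2 |

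**Cells not recorded**

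- Phase I: 0 of 25.
- Phase II: 2 attributions × 2 grades = 4 of 25.
- Phase III: (2 attributions × 3 grades) + (3 attributions × 1 grade) = 6 + 3 = 9 of 25.

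Under the AE definition, log sentence and source-documentation sentence, the count is 0 of 25 whatever the phase. That is the contradiction. These are counts of cells, not of events.

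**Trace of an event that leads to a hold or discontinuation**

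- Grade 2 constipation or abdominal pain judged Possible or higher: recorded under every phase.
- The same event judged Unrelated or Unlikely: recorded under Phase I, outside the table under Phases II and III.
- Grade 3 judged Unrelated or Unlikely: recorded under Phases I and II, outside the table under Phase III. If it is serious, 12.3 still requires a report to the supporting company regardless of causality.

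**Effect on the 11.2 proportions.** Let p be the true proportion of patients in an arm with a given event type. Let q be the share of those patients whose every event of that type falls in an omitted cell.

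- Recorded proportion = p(1 − q), which cannot exceed p.
- With the same q in both arms, the recorded difference is (p_A − p_B)(1 − q), while the ratio p_A/p_B is unchanged.
- If q = 0, nothing is lost.

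The documents give neither p nor q, so the direction is known but the size is not.

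If side effects in 11.2 means related events only, the Phase II entries lose none of them and the Phase III entries lose only Grade 1. In that case the proportion depends on attribution by definition.

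**The case against.** The case against is substantial, and it limits the point in several ways.

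- **The table is only recommended.** A reader might infer that it is the sole rule on recording. It is not: the log and source-documentation sentences stand in the same section without a filter, 12.5 covers all AEs, and 8.14 requires weekly calls until events noted on a call resolve. This stands. The fault is an unresolved contradiction, not a clear instruction to discard events.
- **The phase.** A reader might infer that the protocol fails to state its phase, because the overview says only "Study Type: Prospective Clinical Trial" and the phase mentioned in 11.3 concerns earlier trials (doses that "were used in the phase 3 TELESTAR trial"). Title pages were removed from the text reviewed, so the phase may be stated there and no omission can be charged. A Phase II or Phase III label would still leave the filter in place; only Phase I would remove it.
- **Holds may concern related events only.** The heading of 6.3.2 is limited to drug-related events and its footnote presents constipation and abdominal pain as exceptions to that scheme. On that reading, a Grade 2 event leading to a hold is recorded under every phase. Treatment from Grade 1 in 6.3.3.3 is as clinically indicated, not mandatory. This narrows the gap, but the hold and discontinuation sentences themselves set no attribution condition.
- **Holds are recorded anyway.** Section 6.4 requires dose modifications and interruptions to be captured. That is dosing data and does not guarantee a matching AE entry.
- **Other safeguards exist.** Serious events are reported regardless of causality (12.3), depression is assessed at baseline, 3 and 6 months, and suicidal ideation leads to discontinuation (6.3.3.4) and removal from the study (10.6.4). These cover part of the concern but not non-serious, low-grade events.
- **Blinding.** If blinded attribution is equally selective in both arms, the ratio between arms is preserved. The proportions that 11.2 reports, and their difference, are not.

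**Conclusion.** The contradiction is real and can be verified from the text. Depending on which instruction staff follow, 0, 4 or 9 of the 25 grade-by-attribution cells go unrecorded. An event leading to a hold or discontinuation could lack an AE entry, but only if the Phase II entries (Grade 2) or the Phase III entries (Grade 2 or 3) are applied and the event is judged Unrelated or Unlikely.

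A reader might go further and conclude that the side-effect rates are understated. The documents do not show this: it requires the table to be applied over the log sentence, and it depends on an undefined term in 11.2. The supportable statement is that the proportions may be understated and may depend on the assessor, by an amount that cannot be estimated from the documents.

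This is an inexpensive improvement worth making, not a defect that undermines the trial. The cell counts rest on the table as extracted from PDF, where it is split across a page break; they should be checked against the original layout.

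**What to change.** 1. In 12.1, replace the table with one rule for this trial: every AE of any grade and any attribution is recorded from first dose to 30 days after last dose, with grade and attribution as data fields. These limits match the start of AE collection in 6.2.1 and the SAE window in 12.2.
2. If the sponsor keeps a filter, record regardless of attribution at least every AE that leads to treatment, hold, dose change or discontinuation, plus depression and suicidal ideation.
3. In 11.2, state that the per-arm proportions are all-cause, with related events as a secondary display. This also settles what side effects means.

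The cost is protocol wording and additional AE entry for about 60-80 patients (60 originally planned, maximum 79). Patients already treated need reconciliation from source: the counts in 11.1 imply 28 + 13 + 6 = 47 at the drop-out review. The burden should be modest, because events are already elicited at calls and visits and 12.1 already requires source documentation for all of them. No change to dosing or clinical management is involved.

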12.2 Serious Adverse Event Reporting (SAE)

An adverse event or suspected adverse (possible, probable, and definite AE) reaction is considered “serious” if, in the view of either the investigator or the sponsor, it results in any of the following outcomes:

- Death
- A life-threatening adverse drug experience – any adverse experience that places the patient, in the view of the initial reporter, at immediate risk of death from the adverse experience as it occurred. It does not include an adverse experience that, had it occurred in a more severe form, might have caused death.
- Inpatient hospitalization or prolongation of existing hospitalization
- A persistent or significant incapacity or substantial disruption of the ability to conduct normal life functions.
- A congenital anomaly/birth defect

Important medical events that may not result in death, be life-threatening, or require hospitalization may be considered a serious adverse drug experience when, based upon appropriate medical judgment, they may jeopardize the patient or subject and may require medical or surgical intervention to prevent one of the outcomes listed in this definition. Examples of such medical events include

allergic bronchospasm requiring intensive treatment in an emergency room or at home, blood dyscrasias or convulsions that do not result in inpatient hospitalization, or the development of drug dependency or drug abuse (21 CFR 312.32).

- Important medical events as defined above, may also be considered serious adverse events. Any important medical event can and should be reported as an SAE if deemed appropriate by the Principal Investigator
- All events occurring during the conduct of a protocol and meeting the definition of a SAE must be reported to the IRB in accordance with the timeframes and procedures outlined in "University of Texas M. D. Anderson Cancer Center Institutional Review Board Policy on Reporting Serious Adverse Events". Unless stated otherwise in the protocol, all prompt SAEs, unexpected and related, must be reported to the IRB (within 10 working days of knowledge of the event).
 - The MDACC "Internal SAE Report Form for Prompt Reporting" will be used for reporting
 - Elective admissions or admissions for transfusions will not be considered an SAE.
- Serious adverse events will be captured from the time the patient take his first treatment drug dose until 30 days after the last dose of drug. Serious adverse events must be followed until clinical recovery is complete and laboratory tests have returned to baseline, progression of the event has stabilized, or there has been acceptable resolution of the event.
- Additionally, any serious adverse events that are reported to the treatment team that occur after the 30 day time period that are related to the study treatment must be reported to the IRB. This may include the development of a secondary malignancy.
- Primary investigator and research team may become unblinded to the study arms if it is deemed a medical necessity required for patient treatment or safety.

Reporting to FDA:

It is the responsibility of the PI and the research team to ensure serious adverse events are reported according to the Code of Federal Regulations, Good Clinical Practices, the protocol guidelines, the sponsor's guidelines, and Institutional Review Board policy.

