12.3 Investigator Communication with Supporting Company

All SAEs, regardless of causal relationship to study drug, and pregnancies must be reported to the TerSera Therapeutics within 72 hours of investigational site awareness of the event. Investigators should not wait for complete information on an event before notifying the TerSera Therapeutics of an SAE.

Investigational site personnel must use the approved method of notification per the TerSera Therapeutics to report these events.

If paper report forms are used, the form(s) should be sent to:

Safety Data [contact] or

Email address (in case of fax failure): [contact]

In case of failure of/lack of access to eCRF, email, or fax, the event should be reported to the TerSera Medical Information Call Center within one business day of awareness: [contact]

If an SAE is reported via telephone, the telephone report should be followed by a written report using a reporting method described above (ie, completion of eCRF or paper form).

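### Section 12.2 exempts elective and transfusion admissions without condition, so an adverse event that is serious only because of such an admission falls outside mandatory SAE reporting

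*Combined protocol and SAP*

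**What the plan says.** Section 12.2 starts from the event: "An adverse event or suspected adverse (possible, probable, and definite AE) reaction is considered" serious if it results in any outcome on a list. One outcome on that list, given without exception, is "Inpatient hospitalization or prolongation of existing hospitalization". The section then requires events that meet the definition to be reported to the IRB.

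A later bullet in 12.2 reads: "Elective admissions or admissions for transfusions will not be considered an SAE". Nothing in it refers to why the admission was needed, when it was planned, or whether an adverse event lay behind it.

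Three other provisions bear on the point:

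- Section 12.1, on conditions present at entry: "Medical conditions/diseases present before starting study therapy are only considered adverse events if they worsen after starting study treatment".
- Section 12.2, on events that meet no listed outcome: "Any important medical event can and should be reported as an SAE if deemed appropriate by the Principal Investigator".
- Section 12.3, on notice to the supporting company: "All SAEs, regardless of causal relationship to study drug, and pregnancies must be reported". The time limit is 72 hours from site awareness.

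**The concern.** An exemption of this kind is normally meant to keep planned care for stable conditions out of the SAE file. As worded, this one goes further. It also covers an admission for transfusion, or a scheduled admission, that happens because of something that started or got worse on study drug. Site staff who follow the definition would report such an event, and staff who follow the bullet would not.

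What is at stake is the speed and consistency of safety reporting. IRB reporting, SAE capture from first dose to 30 days after the last dose (12.2), and the 72-hour company notice (12.3) all depend on whether an event is called an SAE. That matters more here because section 11.3 describes a study dose above the approved one and says that toxicity monitoring will not be conducted. This leaves more of the timely safety signal to SAE reports, alongside the DSMB named in section 12.0.

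**Working it through.** No arithmetic applies, because the point depends on no rate, sample size or event count. The check sets the provisions side by side and asks, for each kind of admission, what the definition and the bullet each say.

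| Admission | Adverse event under 12.1? | 12.2 definition | 12.2 bullet |
|---|---|---|---|
| Planned care, pre-existing condition unchanged | No | Not an SAE | Not an SAE |
| Transfusion admission for an event that began after first dose; no other criterion met | Yes | SAE | Not an SAE |
| Scheduled admission because a pre-existing condition worsened after first dose; no other criterion met | Yes | SAE | Not an SAE |
| Either of the two rows above, but fatal, life-threatening or incapacitating | Yes | SAE on that other criterion | Addresses only the admission |
| Unplanned admission, not for transfusion, caused by an adverse event | Yes | SAE | Does not apply |

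The table shows three things.

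1. In the first row the bullet agrees with the definition but adds nothing. Section 12.1 already keeps an unchanged pre-existing condition from being an adverse event, so there is nothing to grade as serious.
2. The two sentences disagree only in the second and third rows. Both situations fall within 12.1: worsening after the start of treatment is expressly an adverse event, and an abnormal laboratory value counts as one if it needs treatment. A fall in blood count that requires transfusion therefore qualifies.
3. It follows that the bullet changes the classification only where an adverse event led to the admission. Those are the cases the hospitalization criterion is there to catch.

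Next, what catches the events in rows two and three if the bullet is followed?

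- **Important medical event (12.2).** This route is open, and an event reported through it goes to the company under 12.3. It applies only if the Principal Investigator deems it appropriate. It also sits awkwardly with the bullet. Its examples include "blood dyscrasias or convulsions that do not result in inpatient hospitalization", so a dyscrasia without an admission is offered as a candidate SAE, while one that leads to a transfusion admission meets a sentence saying that the admission is not an SAE.
- **AE log (12.1) and hospitalization data (8.12).** Both would hold the event. Neither carries the SAE reporting deadlines.
- **FDA paragraph (12.2).** It names federal regulations and good clinical practice, but also the protocol itself, and does not say which prevails. It does not settle the conflict.

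**The case against.** The strongest defence is that the definition concerns events and the bullet concerns admissions, so the bullet can be read as a reminder that an admission with no event behind it is not an SAE. That is probably the intent, and for the first row of the table it is right. It does not rescue the wording, because the bullet does not say so and its plain terms cover admissions that do have an event behind them.

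It can also be said that the bullet stands near the IRB-reporting item and may be meant for that purpose alone. Its wording is general, however, and the layout of the extracted text is not reliable evidence of a narrower scope.

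Other parts of the defence stand, and they limit the point:

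- Fatal, life-threatening or incapacitating events remain SAEs, as do those that the Principal Investigator designates.
- The trial has an AE log, hospitalization data, scheduled toxicity calls (8.14), a by-arm summary of side effects (11.2) and a DSMB (12.0).
- The primary endpoint, power and efficacy analyses are untouched.

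Two stronger readings are tempting. A reader might infer that drug-related bleeding and on-study cardiac surgery are removed from the SAE counts. The documents do not support that. They do not name bleeding as an effect of the drug; the nearest expected event in 12.1 is "coagulation abnormalities". They do not anticipate cardiac surgery on study, and section 5.2.12 lists symptomatic severe valve disease among the exclusions. A life-threatening bleed or an unplanned operation that meets the definition would still count.

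A reader might also try to size the loss from the SAE percentages in section 11.3. Those are 12-week figures from another trial and do not separate types of admission. The plan in 11.2 specifies no analysis of SAE rates that would be biased.

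**Conclusion.** The contradiction is real and narrow. It affects adverse events that began or worsened after first dose and whose only seriousness criterion is an elective or transfusion admission. For these, one sentence of 12.2 requires SAE reporting and another removes it, leaving only a discretionary route.

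The size cannot be estimated. The documents report no such admissions and give no rate for them, so the number affected could be zero. The effect is on the completeness and timing of mandatory reports, since the underlying data are collected elsewhere.

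The conclusion assumes that sites apply the bullet as written. If they already read it as covering only admissions with no adverse event behind them, practice is sound and only the text is wrong. Either way the wording should be corrected, because it produces a wrong classification by rule and the correction is cheap.

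**What to change.** Replace the bullet with wording that ties the exemption to the absence of an adverse event, for example:

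*An admission planned before first dose for a condition that has not worsened is not an SAE. Any other admission, including one for transfusion or a procedure, is judged by the adverse event that led to it and is reported if that event meets the definition above.*

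Then check the hospitalizations already collected under section 8.12 against the revised wording, and report any that now qualify.

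The cost is a one-bullet amendment, a short look-back through data that the trial already holds, and a few more SAE forms.
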